6. TREATMENTS

6.1 TREATMENT ARMS

Arm 1: Control group. Women will be supplied with an app/wearable device (Fitbit) to monitor physical activity, weighing scales and a home blood pressure monitor. They will be asked to record their resting blood pressure, resting heart rate and weight twice a week for 24 weeks.

Arm 2: DNA-based intervention. In addition to the BP and weighing procedures for the control group, women will be supplied with a DNA Nudge wearable device and the accompanying app. They will take a cheek swab for genetic analysis and this will be processed in accordance with the manufacturer's guidelines.

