8.2 TRIAL CLOSURE

9. STATISTICS AND DATA ANALYSIS

10. MONITORING

GLOSSARY OF ABBREVIATIONS

RCT	Randomised Controlled Trial
GDM	Gestational Diabetes Mellitus

POST-GDM-DNA; Post-delivery intervention for weight loss, glycaemia and cardiovascular health

IRAS ID 292085

Protocol v12.1 8/3/22

CI	Chief investigator
TMG	Trial Management Group
GCP	Good clinical practice
HbA1c	Glycated haemoglobin - monitors average blood glucose
HDL	High-density lipoprotein cholesterol
LDL	Low-density lipoprotein cholesterol
BP	Blood pressure

KEYWORDS

Weight, blood pressure, glycaemia, HbA1c, physical activity, wearable, postnatal, post-delivery, DNA, personalised

STUDY SUMMARY

TITLE Post-delivery intervention in women with previous gestational diabetes mellitus for weight loss, glycaemia and cardiovascular health

DESIGN Feasibility study

Allocation: RCT

AIMS To determine the feasibility of a post-delivery intervention to improve glycemia and cardiovascular function and promote weight loss in women who have had gestational diabetes.

OUTCOME MEASURES Primary outcome; Effect of intervention on HbA1c: difference in HbA1c between intervention arm and control arm measured at 12 weeks.

Secondary Outcomes;

- Adherence to intervention;
- Willingness to be randomised to post-delivery intervention;
- Process measures to evaluate patient experience of study and intervention;
- Participants' preferred time to commence the study, within the start date allowance of 6 weeks – 6 month post-delivery.
- Between-arm differences and within-arm differences to evaluate:
 - Effect of intervention on HbA1c at 12 and 24 weeks
 - Effect of intervention on weight and BMI at 12 and 24 weeks
 - Effect of intervention on systolic and diastolic blood pressure at 12 and 24 weeks
 - Effect of intervention on lipid profile (total cholesterol, HDL, LDL) at 12 and 24 weeks
 - Effect of intervention on physical activity at 12 and 24 weeks

POPULATION We will recruit 50 women aged 18-45 with previous gestational diabetes and randomise them to 1 of 2 arms to commence study at 6 weeks – 6 months post-delivery. Women starting the study at 13 weeks post-delivery will have their routine post-delivery HbA1c act as baseline HBA1c.

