3. STUDY DESIGN

We will conduct a feasibility study for an open-label, randomised, controlled trial of a personalised post-delivery intervention (*DNA Nudge*) to improve weight, glycaemia and cardiovascular function in women with previous GDM.

The study is designed to be remote, to enable the study to begin and continue in the pandemic and minimise barriers to recruitment. Study participants will be provided with equipment and instructions to collect samples and measurements at home. Contact with the research team will be over telephone or Microsoft Teams video call.

We will advertise in diabetes antenatal clinics using word-of-mouth, posters, social media and on departmental emails at Imperial College Healthcare NHS Trust or Imperial College POST-GDM-DNA; Post-delivery intervention for weight loss, glycaemia and cardiovascular health IRAS ID 292085

for women with current/previous GDM aged 18-45. We will recruit via Twitter, email and in-person encounters.

We will randomise women to 1 of 2 arms:

Arm 1: Standard dietary and physical activity advice as per NICE guidelines at week 1 (active control arm; n = 25)

Arm 2: DNA-based personalised dietary and physical advice delivered by DNA Nudge dietician at week 1 and by DNA Nudge wearable and app for weeks 1-24 (intervention arm; n = 25)

Women not randomised to DNA Nudge will be provided with an activity app/wearable device (Fitbit) to monitor daily step count. All women will be provided with a home BP monitor and weighing scales.

Week 1

Eligibility assessment, consent, randomisation, IPAQ questionnaire, baseline BP and weight, blood sample collected for baseline lipid profile.

Some women will begin the study at 13 weeks post-delivery and coincide with the routine postnatal HbA1c for women with GDM. The routine post-delivery HbA1c will be baseline HbA1c for this study. For women who commence the study outside the 13 weeks post-delivery window, a finger prick blood sample will be used for a baseline HbA1c test.

Women in the control arm will be given standard dietary and physical activity advice by the research team, in line with NICE guidelines.

Women in the DNA Nudge arm will provide a cheek swab for DNA analysis, carried out by DNA Nudge. They will be given personalised dietary advice by a DNA Nudge dietician, and be provided with DNA Nudge wearable, app and instructions.

Week 6:

Telephone/video-call follow-up to check ongoing willingness to participate and assess adherence.

Week 12:

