Collect weight and BP data from weeks 1-12, collect blood sample for HbA1c and lipid profile. Check ongoing willingness to participate and assess adherence.

Week 18:

Telephone/video-call follow-up to check ongoing willingness to participate and assess adherence.

Week 24:

Collect weight and BP data from weeks 12-24, follow-up IPAQ questionnaire, collect blood sample for HbA1c and lipid profile, return devices and collect usage data from DNA Nudge. Qualitative questionnaire to explore intervention experience.

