8. STATISTICS AND DATA ANALYSIS

A study master list with patient identifiable information will be stored on a password-protected NHS computer in a locked research office at Queen Charlotte's and Chelsea Hospital, accessible only to the research team. This will match patient identifiable information with their study identification number. This study identification number will be used for the study database, which will be a cloud-based Excel database, which will be password protected and accessible only by the research team.

If any health conditions are discovered incidentally during the study they would be discussed with the participant immediately and their consent sought to share the information with their GP for the arrangement of their ongoing healthcare.

The study sample is 50 participants, 25 in each arm. The sample size has been based on guidance from the NIHR on pilot/feasibility studies (12) and the literature that it references that concludes that pilot studies should look for a sample size of at least 50 (13).

Data will be analysed after all participants have completed the 24 study weeks and all data is collected. Patient demographics will be presented as median/range or as categorical data where appropriate. We will evaluate primary and secondary outcomes using descriptive statistics. Between group comparison will be made using logistic regression.

Data and all appropriate documentation will be stored for 10 years after the completion of the study in accordance with ICHT guidance.

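### The plan does not say how the twice-weekly home BP and weight readings form the baseline, week-12 and week-24 values, and states no analysis that uses the series or adjusts for baseline

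*Combined protocol and SAP*

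**What the plan says.** - **Readings.** Section 6.1 asks control women to "record their resting blood pressure, resting heart rate and weight twice a week for 24 weeks". The intervention arm follows the same routine: its own items come "In addition to the BP and weighing procedures for the control group".
- **Collection.** Section 3 retrieves the whole series in two batches: "Collect weight and BP data from weeks 1-12" at the week-12 contact and "Collect weight and BP data from weeks 12-24" at the week-24 contact. Week 12 falls in both batches.
- **Baseline.** Section 3, Week 1, lists "baseline BP and weight, blood sample collected for baseline lipid profile". It does not say how many BP or weight readings make up the baseline.
- **Outcomes.** The Study Summary lists "Effect of intervention on systolic and diastolic blood pressure at 12 and 24 weeks" and "Effect of intervention on weight and BMI at 12 and 24 weeks" among the secondary outcomes, as between-arm and within-arm differences. Section 2 repeats the BP and weight objectives at the same two time points.
- **Analysis.** The Statistics and Data Analysis section (numbered 8 in the body, 9 in the contents list) says "We will evaluate primary and secondary outcomes using descriptive statistics". It then names logistic regression for the comparison between groups. It names no covariates and no repeated-measures method.

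**The concern.** The outcome is a value at week 12 and at week 24, while the data are a series of about 48 readings. Nothing connects the two. The week-12 value could be the last reading before the contact, the reading nearest a target date, a weekly mean, a wider window mean or a model estimate. There is no window, no minimum number of readings and no rule for a missed one.

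The stated between-group method does not fill the gap. Logistic regression ordinarily models a binary outcome, and the plan gives no cut-point for BP or weight. The within-arm differences presumably need a baseline, but no baseline adjustment is stated for the comparison of arms.

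Three things are at stake:
- **Reproducibility.** Two analysts could follow the plan and report different BP effects. The trial is open-label and the readings are self-recorded, so a definition settled after the data are seen is hard to defend.
- **Precision.** With 25 women per arm, a narrower interval at almost no cost is worth having.
- **Use in a later trial.** An SD from single readings differs from an SD of averaged readings. If the value is undefined, so is the SD handed on.

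**Working it through.** **Inputs from the documents.** Two readings a week for 24 weeks (Section 6.1) gives 2 × 24 = 48 scheduled readings per woman. A two-week window holds 2 × 2 = 4, and week 1 holds 2. There are 25 women per arm (Statistics section). The documents give no precision figure for BP or weight, and no SD, reliability or correlation, so there is no plan figure to reproduce.

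**Assumptions.** ρ is the correlation between two readings from the same woman, which is also the reliability of one reading. I take 0.5 to 0.8 for BP and 0.98 as a weight-like value, with equal correlation between all readings unless stated. Variances are in units of the variance of one reading. All 50 women are assumed to contribute full data. The degrees of freedom stay at 48, ignoring the one lost to a covariate.

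**Step 1: one reading, follow-up only.** The 95% half-width for the arm difference is t(48) × √(2/25) = 2.011 × 0.283 = 0.57 SD.

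**Step 2: mean of four readings, follow-up only.** V = ρ + (1 − ρ)/4. The half-width is 0.57 × √V, the narrowing is 1 − √V, and the equivalent sample size is 1/V.

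| ρ | V | Half-width (SD) | CI narrower by | 1/V |
|---|---|---|---|---|
| 0.5 | 0.625 | 0.45 | 21% | 1.60 |
| 0.7 | 0.775 | 0.50 | 12% | 1.29 |
| 0.8 | 0.85 | 0.52 | 8% | 1.18 |
| 0.98 | 0.985 | 0.56 | 0.8% | 1.02 |

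The variance is halved only if ρ is below (0.5 − 0.25)/(1 − 0.25) = 0.33.

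**Step 3: add baseline adjustment.** With one baseline and one follow-up reading, V = 1 − ρ². With two baseline readings (week 1) and four follow-up readings, V = (1 − ρ)[1/4 + ρ/(1 + ρ)].

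| ρ | V, 1 baseline + 1 follow-up | Half-width (SD) | V, 2 baseline + 4 follow-up | Half-width (SD) |
|---|---|---|---|---|
| 0.5 | 0.75 | 0.49 | 0.292 | 0.31 |
| 0.8 | 0.36 | 0.34 | 0.139 | 0.21 |
| 0.98 | 0.040 | 0.11 | 0.015 | 0.07 |

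**Step 4: weight with slow drift.** Equal correlation flatters averaging for weight, because neighbouring readings move together. Assume variance shares of 0.95 stable, 0.045 drifting (correlation 0.95 per week) and 0.005 noise. The correlation between baseline and week 12 is then 0.95 + 0.045 × 0.95¹² = 0.974.
- Averaging four readings, follow-up only: V = 0.995.
- Adjusting one follow-up reading for one baseline reading: V = 1 − 0.974² = 0.051.
- Two baseline and four follow-up readings on top of that: a further factor of 0.791, so V = 0.791 × 0.051 = 0.040.

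So for weight, adjustment takes the variance from 1 to about 0.05, and averaging removes only about another 0.01.

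**Step 5: what averaging must not do.** A mean of all 48 readings, or a mixed model with one overall arm effect, estimates an average effect over 24 weeks. The outcomes are the effects at weeks 12 and 24, so any model on the full series needs an arm contrast at each of those times.

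**The case against.** The strongest reply is that no inferior method has been specified, so there is nothing to improve on. The documents nowhere say that one reading per time point is used or that the rest are dropped. They retrieve the full series, and naming two time points is compatible with a window mean. A reader might infer a single-reading rule, but the text does not state one. That much stands. The reply does not reach the remaining gap: the Statistics section names no analysis that would use the series, and its between-group method does not suit these continuous outcomes.

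A reader might also infer that most of the precision is being lost, since 2 of 48 readings is 4%. The documents do not support this. Readings from one woman are correlated, and at reliability 0.5 to 0.8 a single reading already holds 62.5% to 85% of the information in a mean of four. For weight it holds nearly all of it.

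On choosing a reading after the fact, Section 5.2 keeps the data analysis blind to arm until completion. This limits picking a value because it favours one arm. It does not define the value or remove the analyst's discretion.

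Finally, these are secondary outcomes in a 50-woman feasibility study, and no stated decision depends on BP or weight precision. That is fair and limits the weight of the point. It is not a reason to leave the values undefined when the remedy costs so little.

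**Conclusion.** The point holds in this form: the plan schedules and collects a repeated BP and weight series, does not say how it becomes the baseline, week-12 and week-24 values, and states no between-arm analysis that uses either the repeats or the baseline. This goes a little beyond missing wording, because a concrete and better-suited analysis is available from data already collected.

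The size is modest. For BP, a full four-reading mean narrows the follow-up-only CI by about 21% at reliability 0.5 and about 8% at 0.8. Both are upper figures for those reliabilities, since women with fewer than four readings gain less. For weight, averaging alone narrows it by under 1%, and most of the gain comes from baseline adjustment. All these figures rest on assumed correlations.

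The equivalent of 60% more women is the favourable end of the assumed BP range and should not be quoted alone. The HbA1c comparison is untouched. The change should be made before analysis, but it does not threaten the study.

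**What to change.** Add to the Statistics section, before any unblinded analysis:

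1. **Baseline:** the mean of the available week-1 readings, separately for systolic BP, diastolic BP and weight. State whether week-1 readings taken after the advice session count.
2. **Follow-up values:** the mean of all readings in weeks 11-12 for the week-12 value and in weeks 23-24 for the week-24 value (up to four each), with at least one required. Report how many readings each woman contributed. BMI follows from the averaged weight.
3. **Comparison of arms:** for these continuous outcomes, replace logistic regression with a linear model (ANCOVA) of the follow-up value on arm and baseline. Report the adjusted difference with its 95% CI.
4. **Optional support:** a mixed model on all twice-weekly readings, with time in the model, reporting the arm difference at weeks 12 and 24 and not a 24-week average.
5. **For a later trial:** give the SD of the window means and the within-woman correlation, so that the assumption used here can be replaced by an estimate.

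The cost is a short amendment to the analysis text and a little more programming, with no new data and no added burden on participants. The one trade-off is that each value then represents a two-week window and not a single day.

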7. ADVERSE EVENTS

No adverse events are anticipated in this study.

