4. PARTICIPANT ENTRY

4.1 PRE-RANDOMISATION EVALUATIONS Women replying to our adverts will be assessed for eligibility by questionnaire.

4.2 INCLUSION CRITERIA Pregnant women with gestational diabetes (women will be given the option to start the study between 6 weeks and 6 months post-delivery) or women who have given birth in the last 12 months and had gestational diabetes during that pregnancy, aged 18-45, access to a smartphone with an operating system of iOS 9.0 or above, or Android 5.0 or above [CB: operating systems correct as of 23/03/21]

4.3 EXCLUSION CRITERIA Diabetes outside of pregnancy (diagnosis of type 1 or 2 diabetes; or HbA1c 48 mmol/mol or above). Health contra-indications to moderate-vigorous exercise. Planning pregnancy during the study period or become pregnant during the study period. Cancer, kidney disease, liver disease, or pancreatitis. Have had gastric bypass surgery or similar weight loss surgery.

4.4 WITHDRAWAL CRITERIA If women withdraw consent or become pregnant during the study period, the data collected to that point will be retained, they will be withdrawn from the study and we will request permission to collect safety outcomes from them.

If they agree to participate, consent will be gained and stored in the site file.

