7.2 REPORTING PROCEDURES

All adverse events should be reported. Depending on the nature of the event the reporting procedures below should be followed. Any questions concerning adverse event reporting should be directed to the Chief Investigator in the first instance.

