10. MONITORING

10.1 RISK ASSESSMENT

This study uses a commercially available DNA analysis product used in-keeping with the manufacturer's guidelines. This study recommends exercise in accordance with the UK Chief Medical Officer's recommendations. This study supplies commercially available products for home blood pressure, weight and activity monitoring. As such it is considered low risk.

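### All adverse events must be recorded, but no scheduled contact asks about them and no safety outcome is defined, so a low count could not be interpreted

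*Combined protocol and SAP*

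**What the plan says.** Section 7 begins "No adverse events are anticipated in this study". Section 7.1 then defines an adverse event broadly, with no requirement that the study caused it. Section 7.2 states "All adverse events should be reported", section 7.2.1 extends recording to all non-serious events, and section 7.2.2 asks for a serious event form within 24 hours.

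Section 3 describes a remote study: "Contact with the research team will be over telephone or Microsoft Teams video call". The week 6 and week 18 contacts have the same content: "Telephone/video-call follow-up to check ongoing willingness to participate and assess adherence". Week 12 adds weight and blood pressure data and a blood sample, then "Check ongoing willingness to participate and assess adherence". Week 24 lists measurements, a blood sample, the activity questionnaire, return of devices with usage data, and a questionnaire on experience of the intervention.

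Safety outcomes are mentioned once, in section 4.4, for women who withdraw consent or become pregnant: "they will be withdrawn from the study and we will request permission to collect safety outcomes from them". They are not defined there or elsewhere. Under section 8.1, women lost to follow-up are taken out of the study, and no safety enquiry is described for them. Safety is absent from the outcome measures in the Study Summary, from the objectives in section 2 and from the Statistics and Data Analysis section.

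**The concern.** The protocol sets a duty to record every event but gives no step by which the team would learn of one. In a trial run by telephone and video, the scheduled calls are the natural place to ask, and their listed content does not include the question. Any event that is recorded also has no stated place in the results.

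Two things are at stake. The first is interpretation: a low or zero count could mean that little happened or that nobody asked. Because the women know their allocation (section 5), unprompted reporting could also differ between arms, so a comparison of counts would be hard to read. The second is the serious event pathway: the 24-hour form cannot be started for a hospital stay that the team does not know about.

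**Working it through.** **Step 1: set the duty beside the schedule.**

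| Place | What is listed | Adverse event question? |
|---|---|---|
| 7.2, 7.2.1 | Report and record all events | Duty only; no method |
| Week 6 | Willingness, adherence | No |
| Week 12 | Weight, blood pressure, HbA1c, lipids, willingness, adherence | No |
| Week 18 | Willingness, adherence | No |
| Week 24 | Weight, blood pressure, HbA1c, lipids, activity and experience questionnaires, device return | No |
| Outcomes, objectives, analysis | Efficacy, adherence, experience | No safety item |

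**Step 2: look for other routes by which events could come to light.**

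- Section 4.4: a request for safety outcomes, but only after withdrawal of consent or pregnancy.
- Statistics and Data Analysis: health conditions found by chance are discussed with the woman and, with her consent, shared with her GP. No link to adverse event recording is stated.
- Sections 3 and 6.1: scheduled blood pressure, weight, heart rate, HbA1c and lipid data. No value is defined as an adverse event.
- Week 24 experience questionnaire: its content is not given.

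These routes are real, but none is a general enquiry made of every woman who remains.

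**Step 3: what a zero count would show.** The documents give no adverse event rate and no safety calculation, so there is no figure to reproduce. The one relevant input is the sample size, 25 per arm and 50 in total (section 3; Statistics and Data Analysis).

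With complete ascertainment, the one-sided 95% upper bound after zero events in n women is 1 − 0.05^(1/n):

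- One arm: 1 − 0.05^(1/25) = 0.1129, or 11.3%.
- Both arms: 1 − 0.05^(1/50) = 0.0582, or 5.8%.

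The two-sided 95% versions, with 0.025 in place of 0.05, are 13.7% and 7.1%.

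**Step 4: incomplete ascertainment (illustration only).** Let s be the chance that a woman with an event has it recorded. The bound then applies to s times the true rate, so the bound on the true rate is 0.1129/s per arm. The documents give no s; the values below are assumptions.

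| Assumed s | Bound on true rate after 0/25 | Chance of 0/25 recorded if true rate is 10% (assumed): (1 − 0.10 × s)^25 |
|---|---|---|
| 1 | 11.3% | 7.2% |
| 0.5 | 22.6% | 27.7% |
| 0.25 | 45.2% | 53.1% |
| 0.1 | none (0.1129/0.1 exceeds 1) | 77.8% |

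**The case against.** The best case for the plan has five parts.

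- **Detection does not rest only on a woman volunteering an event.** A reader might infer that it does. The routes in step 2 show otherwise, so the documents support only that detection is largely passive among those who stay.
- **The protocol does not assume that there will be no events.** A reader might take the opening of section 7 that way, but the sections after it define events and set reporting rules. Section 7.2.2 treats an event as unexpected when the protocol does not list it as expected. Read with that rule, the opening sentence works as an empty list of expected events, and every related serious event goes to the ethics committee.
- **There is no contradiction with sections 4.3 and 10.1.** A reader might see one, since section 4.3 excludes women with "Health contra-indications to moderate-vigorous exercise" and section 10.1 says "This study recommends exercise in accordance with the UK Chief Medical Officer's recommendations". Excluding women at risk is a reason to expect few events among those enrolled. Section 10.1 goes on to classify the study as low risk, and section 3 gives activity advice to both arms.
- **No safety conclusion is planned, and the trial is small.** Tolerability is not a stated objective. The 11.3% bound reflects 25 women per arm and would remain even if every event were found. The 22.6% and 45.2% figures rest on assumed ascertainment.
- **Section 3 is a summary.** The case report forms are not part of the documents, and the consent pages are not available for review, so instructions to participants about reporting events cannot be checked.

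All five points narrow the finding and the first three rule out stronger versions of it. None supplies an enquiry at the scheduled contacts or a place for events in the results.

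**Conclusion.** The point holds in this form: the protocol requires all adverse events to be recorded but specifies no enquiry at weeks 6, 12, 18 or 24 and no safety outcome. Detection in women who remain is largely passive, and a low or zero count could not be interpreted.

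The only size that follows from the documents is the best case: 0/25 excludes true rates above 11.3% per arm (one-sided 95%), assuming that all 25 women are followed and every event is found. Under the schedule as written the bound is weaker by an amount that cannot be stated. It would be too strong to say that a clean record carries no information; its information cannot be quantified. That a hospital stay could miss the 24-hour form is a plausible consequence of the schedule, not something the documents show to have happened.

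This should be corrected, but it does not undermine the HbA1c comparison.

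**What to change.** - Add one identically worded question to the week 6, 12, 18 and 24 contacts in both arms: any new illness, injury, hospital attendance or new diagnosis since the last contact. Record the answer, including a negative one, so that the number of women asked is known.
- Add to the secondary outcomes and the analysis the number of women with any adverse event and with any serious adverse event, by arm, to week 24, with exact confidence intervals.
- Use the same list to define the safety outcomes in section 4.4.
- Leave the opening sentence of section 7 as it is. Naming anticipated events there would make them expected under section 7.2.2 and could take related serious events of that kind out of ethics committee reporting.

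The cost is a short protocol amendment, one extra item on contacts already planned, and more minor events to log. The small sample remains a separate limit that this change does not remove.
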